Study protocol with statistical analysis plan

Fostering sustainable dietary habits through optimized school meals –
OPTIMAT

Date: November 14, 2019

Introduction

Public school meals have been highlighted as a suitable setting for children to internalize sustainable dietary habits, which may persist throughout life [1, 2]. Radical changes to food production and consumption are needed to ensure the attainment of Agenda 2030 for Sustainable Development [3], and fulfillment of the Paris Agreement [4]. Planning of school meals must take many aspects into account: health promotion, environmental impact, acceptability by the consumers and affordability to those paying for the meals. Currently many schools use organic products, recycle food packaging and aim to reduce food waste, but environmental impacts like greenhouse gas emissions (GHGE) have so far not received much attention.

In Sweden, fully subsidized lunches are served daily in primary schools to all 1.3 million children aged 6 to 15 [5]. Due to their reach and scale (approximately 230 million meals/year at an annual cost of around 5.6 billion SEK), school meals have enormous potential to increase children's knowledge about health and sustainability, foster sustainable dietary habits and to enable sustainable public procurement.

This study aimed to: a) apply linear programming to develop a GHGE-reduced, nutritionally adequate, and affordable four-week lunch menu plan optimized for minimum deviation from the current food supply; and b) evaluate the climate impact of the menu, effects on food waste, food consumption, and pupils' satisfaction with school lunches. Our hypothesis is that school meals can be optimized to be nutritious and more climate friendly, without negatively affecting acceptance, food waste and cost.

Methods

Design

An interrupted time series (ITS) analysis design will be used to compare the effect of an optimized menu to the baseline menu on daily food waste and consumption at school level. For a baseline period of four weeks children in primary schools will receive a baseline menu. After a two-week break, the optimized four-week menu will be served (intervention period).

Recruitment of schools

During the fall of 2018, public meal managers in three municipalities of Stockholm, Sweden, were invited to information meetings about the intervention. The public meal managers were asked to attend the meeting together with school chefs from primary schools had shown interest in sustainability issues. To be eligible for the intervention, schools were required to have on-site kitchens. They also needed to be able to provide previously used recipes for a standard four-week menu electronically.

Optimization

Recipes for an original (baseline) four-week school lunch menu plan previously served at the recruited schools, will be obtained through the municipality's electronic meal planning system. The foods included and amounts are considered as the baseline food supply. Each food item included has a code that can be coupled to the Swedish national food database and a national climate database for foods containing life cycle data for each food item [6]. This baseline food supply will be optimized using linear programming.

The optimized food list, not including new foods or excluding foods from the baseline list, will be handed to a professional meal planner who develops a new menu plan for the intervention using all foods on the optimized list.

Outcomes

To assess the effect of the new menu plan, data on food waste and consumption will be collected in each intervention school four weeks before (baseline) as well as during the four-week intervention with a 2-week break in between measurement periods. A tool for measuring food waste in school restaurants developed by the National Food Agency in Sweden will be used. The tool requires weighting (using school kitchen scales) of all kitchen waste (both preparation waste and cooking waste); all food prepared in the kitchen; the share of the prepared food that is not eaten and has to be thrown away (serving waste); the share that can be saved; and plate waste. The number of plates used daily by the pupils in the school restaurant will also be recorded. These measurements will be made daily by the personnel in the school kitchens during the baseline as well as during the intervention period. Based on these measurements, the total food consumption (kg) will be calculated as the total amount of food prepared in the kitchen (kg) minus the total amount of prepared food that is not eaten and has to be thrown away (overall waste in kg), the total amount of plate waste (kg), and the total amount of food that could be saved (kg). Plate waste per pupil (g) will be calculated for each day by dividing the total amount of plate waste by the total number of plates used. Similarly, the consumption per pupil (g) will be calculated for each day by dividing the total consumption by the total number of plates used.

Data on school meal satisfaction will be collected at each intervention school through an online questionnaire at baseline and during the last week of the intervention period. Pupils in grades 5 and 8 answer the questionnaire containing ten questions related to the school lunch. Five of the ten multiple-choice questions specifically cover their general (i.e. not for that specific day of week) sense of satisfaction with the school lunch. The questions include how often they consider that the school lunch tastes good, how many days per week that they tend to eat from the school lunch, how often they usually feel full after having eaten lunch, and how often they tend to throw away food in the school restaurant. They are also asked to provide an overall rating of the school lunch.

Qualitative study

Six focus group discussions (FGD) with pupils in grades 5 and 8 and three FGDs with meal staff will be conducted to explore their experiences with the intervention as well as the barriers and facilitators to scaling up.

Statistical analysis plan

In order to compare food waste and consumption between the two periods (baseline and intervention), interrupted time-series (ITS) analysis will be used [7]. ITS analysis will be implemented at school level to assess the difference between the two periods daily in the number of pupils consuming lunch (n), kitchen waste (kg), prepared food (kg), serving waste (kg), total plate waste (kg), plate waste per pupil (g), total consumption (kg), and consumption per pupil (g).

The ITS analysis will be based on linear regression models [7]. These models will be determined by three independent variables: (a) A time-variable, applied to adjust for a potential baseline trend; (b) A variable indicating whether the data point represented the baseline or intervention period to assess the level (mean) change resulting from the intervention; and c) an interaction term between (a) and (b) specifying

the slope change resulting from the intervention. Assumptions of normality, homoscedasticity, as well as absence of autocorrelation and partial autocorrelation will be assessed.

The effect of the new menu plan on the five questions related to school meal satisfaction will be explored with Pearson's chi-squared tests (χ^2) within each intervention school.

The software R (version 3.6.1) [8] will be used for statistical analysis.

Qualitative content analysis [9] will be used to analyze the FGDs.

References

3. UN General Assembly (2015) Transforming our world : the 2030 Agenda for Sustainable Development. UN General Assembly
4. (2015) Paris Agreement. UNFCCC

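### The hypothesis is that acceptance, food waste and cost do not worsen, but the planned analyses only assess differences, give no rule for judging worsening, and leave the ITS level-change coefficient undefined

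*Combined protocol and SAP*

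**What the plan says.** **Hypothesis and aims (Introduction).** The hypothesis is that meals can be made nutritious and more climate friendly "without negatively affecting acceptance, food waste and cost". Aim (a) is to develop a "nutritionally adequate, and affordable four-week lunch menu plan". Aim (b) is to "evaluate the climate impact of the menu, effects on food waste, food consumption" and pupils' satisfaction.

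**Data (Outcomes).** Daily kitchen measurements cover four weeks before and four weeks during the intervention, "with a 2-week break in between measurement periods". Pupils in two grades answer a questionnaire at baseline and in the last intervention week.

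**Analysis (Statistical analysis plan).** "ITS analysis will be implemented at school level to assess the difference between the two periods daily" for eight outcomes, listed without ranking. The linear model has three terms: "A time-variable, applied to adjust for a potential baseline trend"; a period indicator "to assess the level (mean) change resulting from the intervention"; and their interaction, for the slope change. Autocorrelation is to be checked. The five satisfaction questions are explored with chi-squared tests inside each school.

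The documents give no primary outcome, significance level, confidence-interval rule or largest acceptable worsening. They do not say how time is coded or whether the break counts on the time axis. Neither Outcomes nor the Statistical analysis plan mentions a cost comparison.

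**The concern.** A hypothesis of no worsening is supported by estimates precise enough to rule out a worsening that matters. A test of difference that fails to reach significance does not do this, because it may only reflect few data.

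Three further gaps make the hypothesis hard to judge:

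- **Waste.** Four of the eight ITS outcomes are waste measures (kitchen, serving, total plate, plate per pupil). Each has a level and a slope coefficient, so each school yields 4 × 2 = 8 waste coefficients. If level falls while slope rises, or plate waste rises while serving waste falls, the plan does not say whether waste worsened.
- **Acceptance.** A chi-squared test has no direction. A significant result does not show that satisfaction fell, and a non-significant one does not show that it held.
- **Contrast.** The coefficient that is meant to carry the level change is not the mean change unless time is centred suitably, and no centring is stated.

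At stake is whether the report can say anything about half of its hypothesis, and whether two analysts following the plan would report the same level change.

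**Working it through.** The plan has no sample size, power or margin calculation, so there is no figure to reproduce. What follows is an illustration for one school.

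**Inputs.** From the documents: four weeks per period, a two-week break, and a linear model with time, period and their interaction. Assumed: five school days a week (20 + 20 days; break = 10 school days), daily residual SD *s*, independent errors, two-sided 5%, and a constant true rise in waste of 1*s* with no trend change. The documents give no SD, so results are in units of *s*.

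**Step 1: what the period coefficient measures.** Write y = b0 + b1·t + b2·P + b3·(P × t), with P = 1 in the intervention period. The gap between the two fitted lines at time t is b2 + b3·t, so b2 is the gap at t = 0. With days numbered from 1, that is the day before baseline starts. If the interaction is P × (t − c), b2 becomes the gap at t = c. Setting c to the mean intervention day gives the average change over the intervention days.

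**Step 2: its standard error.** The model is equivalent to two separate lines. With 20 days each, Sxx = 20 × (20² − 1)/12 = 665, and

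Var(gap at c) / s² = 1/20 + 1/20 + [(c − m1)² + (c − m2)²] / 665.

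Here m1 = 10.5, and m2 = 30.5 (break not counted) or 40.5 (break counted). The first intervention day is 21 or 31.

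- Uncentred (c = 0): 0.1 + (10.5² + 30.5²)/665 = 1.665, SE 1.29*s*; with the break counted, 0.1 + (10.5² + 40.5²)/665 = 2.732, SE 1.65*s*.
- First intervention day: 0.1 + (10.5² + 9.5²)/665 = 0.402, SE 0.63*s*; counted, 0.1 + (20.5² + 9.5²)/665 = 0.868, SE 0.93*s*.
- Intervention mean: 0.1 + 20²/665 = 0.702, SE 0.84*s*; counted, 0.1 + 30²/665 = 1.453, SE 1.21*s*.

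**Step 3: chance of a non-significant result at a true rise of 1*s*.** This uses the noncentral t with 40 − 4 = 36 df, critical value 2.028 and noncentrality 1/SE (SE in units of *s*). The last column is the chance, if the menu changes nothing, that the 95% CI excludes a rise of 1*s*.

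| Contrast | SE/*s* (break not counted / counted) | Non-significant | CI excludes 1*s* if no change |
|---|---|---|---|
| Uncentred, day 0 | 1.29 / 1.65 | 88% / 91% | 11% / 9% |
| First intervention day | 0.63 / 0.93 | 66% / 82% | 34% / 18% |
| Intervention mean | 0.84 / 1.21 | 79% / 87% | 21% / 12% |

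**Step 4: sensitivity.** AR(1) correlation of 0.2 to 0.4 raises the non-significant rates to 73–88% (first day) and 83–91% (mean). A plain difference of period means has SE √(2/20) = 0.316*s* and misses the rise 13% of the time, but it assumes no trend. A trend of 0.05*s* per school day would shift it by 20 × 0.05 = 1.0*s* or 30 × 0.05 = 1.5*s*. So the choice of contrast matters.

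**Step 5: cost.** Affordability is a design goal in aim (a) and cost is in the hypothesis. The menu actually served is written afterwards by a meal planner from the optimized food list (Optimization). No section then compares the cost of the two menus.

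**The case against.** **The study is an estimation exercise.** The hypothesis is a broad statement of feasibility, aim (b) is to evaluate, and the analysis assesses and explores. No non-inferiority claim is declared. This largely stands. A reader might infer that the investigators will take a non-significant result as proof of no harm, but nothing in the documents says so. What remains is that the hypothesis is worded as no worsening and the plan gives no way to judge it.

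**The illustrated rates measure the short series, not the missing rule.** This stands. They would be the same with a margin and a primary outcome in place, and the 1*s* rise is an arbitrary choice. A reader might infer that stating a margin would cure the imprecision; it would not. The rates show only why a null result would be uninformative.

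**Describing the period term as a mean change signals the intent.** It does, and that supports centring at the intervention mean. But the interaction as written has no centring, so a literal fit would not deliver that quantity.

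**Autocorrelation is already to be checked.** True. Only the action to take if it is found is missing.

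**Menu cost is mostly a calculated property of the menu, not an inferential outcome.** Agreed. It needs a descriptive comparison, not a test or a margin.

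**Conclusion.** The point holds in this form: the plan as written cannot support the no-worsening part of its hypothesis, because it assesses only differences, ranks no outcome, gives no rule for reading the results and describes no cost comparison. Separately, the coefficient meant as the level (mean) change is, under an uncentred interaction, an extrapolation to day 0. Neither conclusion depends on the assumed numbers.

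The size is illustrative. For a rise of one daily SD in one school, a non-significant result is expected 66% to 91% of the time, depending on the contrast and the coding of the break. This assumes 20 + 20 school days, independent errors and two-sided 5%. The documents give no SD, number of schools or tolerable worsening, so no firmer figure is possible.

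The documents do not support the stronger readings that the study is a failed non-inferiority trial, that a null result is planned to count as success, or that the data would be unusable. The point should be settled before analysis; the data collection can stand.

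**What to change.** Before analysis:

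1. **Report estimates.** Give every level and slope change with a 95% CI, and for each satisfaction item the before-after difference in the share of favourable answers (categories listed in advance) with a 95% CI. State that non-significance will not be read as no worsening, and word the hypothesis as estimation.
2. **Define the level change.** Centre the interaction at a stated intervention time point; the intervention mean matches the plan's own description of the term. State whether the two-week break counts on the time axis. Use autocorrelation-robust standard errors if the planned check finds autocorrelation.
3. **Rank the outcomes.** Name one main waste outcome, for example the planned plate waste per pupil, and one acceptance item, the overall rating. Label the rest exploratory.
4. **Optional rule.** Only if a largest acceptable worsening can be justified in advance, conclude that an outcome was not negatively affected when the 95% CI excludes that worsening. Otherwise report the result as inconclusive.
5. **Cost.** Report cost per portion for both menus descriptively if price data exist, or remove cost from the hypothesis. For the baseline side, the plan already obtains "Recipes for an original (baseline) four-week school lunch menu plan previously served at the recruited schools".

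**What it costs.** No new waste or questionnaire data are needed. The cost item needs price data; the rest needs decisions and a few lines of text. The school-level analyses stay as planned. The drawback is that results may well be inconclusive. With an illustrative limit of 1*s* and no true change, one school's CI for the average change would exclude the limit only 12% to 21% of the time. The first-day contrast is more precise (18% to 34%) but describes only the start of the intervention.

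### In schools with both grades, the satisfaction test as written does not separate grade 5 from grade 8, so a shift in grade mix can create or mask a change in acceptance

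*Combined protocol and SAP*

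**What the plan says.** The Outcomes section states that "Pupils in grades 5 and 8 answer the questionnaire containing ten questions related to the school lunch". The data are collected "through an online questionnaire at baseline and during the last week of the intervention period". On content, "Five of the ten multiple-choice questions specifically cover their general (i.e. not for that specific day of week) sense of satisfaction".

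The whole quantitative plan for these items is one sentence in the Statistical analysis plan: the effect of the menu on the five items "will be explored with Pearson's chi-squared tests (χ^2) within each intervention school". School is the only stratum named. The plan does not mention grade, linking of a pupil's two answers, a target response rate, or response counts by grade. It does not say that every school has both grades.

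Grade appears once more, under Qualitative study: "Six focus group discussions (FGD) with pupils in grades 5 and 8". The hypothesis in the Introduction is that the menu can be improved "without negatively affecting acceptance, food waste and cost".

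**The concern.** A two-round table that ignores grade mixes three things: the change within grade 5, the change within grade 8, and any change in the proportion of answers that come from each grade. Nothing in the plan holds that proportion constant. If it moves and the grades differ in satisfaction, the table moves even when no pupil has changed their view. A real fall can be made to look smaller or larger in the same way. If the grades react in opposite directions, the combined table understates both reactions.

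This matters because it is the only planned quantitative analysis of pupils' satisfaction, and the hypothesis claims no loss of acceptance. For a claim of that kind, an analysis that can hide a loss is the more damaging failure.

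**Working it through.** The documents give no respondent numbers, satisfaction levels, response rates or significance level, so there is no figure of the plan's own to reproduce. Everything below is an illustration on assumed inputs: one school with both grades, one item reduced to satisfied or not, 100, 150 or 200 answers per round, and a two-sided 5% test.

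**Formula.** Let p5 and p8 be the baseline proportions satisfied, d5 and d8 the true changes, and w0 and w1 the grade 5 share of respondents in each round. Then

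pooled change = w1·d5 + (1 − w1)·d8 + (w1 − w0)·(p5 − p8).

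The last term is the artefact: mix change times grade gap. It is zero if either factor is zero.

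**No menu effect (d5 = d8 = 0).** Simulated rejection rates of the pooled test:

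| Assumed setting | Artefact | n = 100 | n = 150 | n = 200 |
|---|---|---|---|---|
| Low: 60% v 50%, grade 5 share 50% to 55% | 0.05 × 0.10 = 0.5 points | 5.4% | 5.5% | 5.0% |
| Middle: 60% v 40%, share 50% to 60% | 0.10 × 0.20 = 2 points | 6.1% | 6.7% | 6.5% |
| Top: 60% v 30%, share 50% to 65% | 0.15 × 0.30 = 4.5 points | 9.4% | 12.5% | 13.8% |

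The Mantel-Haenszel test stratified by grade stays at about 5% in every cell. The low row cannot be told apart from a test with no artefact, since counts are discrete.

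**A real fall of 10 points in both grades, with the top-row mix shift.** Pooled change = −10 + 0.15 × 30 = −5.5 points. The pooled test detects it 12%, 15% and 18% of the time at 100, 150 and 200 per round; the stratified test does so 31%, 44% and 55%. If the mix moves the other way (grade 5 share 50% to 35%), the pooled change is −10 − 4.5 = −14.5 points and the fall is exaggerated instead.

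**Opposite reactions, equal and constant grade shares.**

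- +10 and −10 points: 0.5 × 10 − 0.5 × 10 = 0. From 60% in both grades, the pooled and Mantel-Haenszel tests both reject about 5% of the time. The two grade-specific chi-squared statistics summed on 2 df reject 24%, 34% and 44%.
- +15 and −5 points: 0.5 × 15 − 0.5 × 5 = 5, so cancellation is only partial. From 50% in both grades at 150 per round, the pooled and Mantel-Haenszel tests both reject about 15%, and the 2-df sum about 40%.

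The stratified test therefore deals with the mix, but does not reveal opposite reactions.

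**Cost in power.** With no grade gap, no mix change and a 15-point fall, the pooled and stratified tests have about 76% and 75% power at 150 per round.

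**Cost in precision.** With equal grades, each grade-specific estimate uses half the answers, so its interval is √2 ≈ 1.41 times as wide, about 40% wider.

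**The case against.** The strongest reply is that the plan is silent on grade rather than wrong. It nowhere says that grades are combined, the items are only to be explored, no decision rule hangs on them, and for moderate inputs the distortion is small. Most of this stands. Pooling is the plain reading of a plan that names only school, not a stated rule. The 9 to 14% rates need the largest assumed gap and the largest assumed mix change together; in the middle of the range the excess over 5% is one to two points. Exact cancellation needs opposite effects of equal weighted size. In a school with only one of the two grades the issue does not arise.

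A reader might go further in three ways that the documents do not support.

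- That dissatisfied older pupils will drop out, so that the bias runs towards hiding a loss. Nothing says that grade 8 is less satisfied, or that response differs by grade or round. The direction is unknown.
- That the focus groups show the grades were meant to be studied separately. The Qualitative study section names both grades but gives one shared purpose, and does not say that the groups are split by grade.
- That stratifying answers every question about who responded. It does nothing about a change in who answers within a grade.

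The reply does not remove the need to specify. A statistician following the text would build one table per item and school, and nothing in the plan would then expose a change in mix or a difference between grades.

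**Conclusion.** The point holds in a limited form. As written, the satisfaction analysis gives no protection against a change in grade mix between rounds and no view of each grade's reaction, in any school that has both grades. Over the assumed ranges (grade gap 10 to 30 points, mix change 5 to 15 points, 100 to 200 answers per round), the effect runs from negligible to a 4.5-point artefact, with false-positive rates up to about 14%. It can create or mask a change in acceptance, in either direction. Both a gap and a mix change are needed, and the documents give evidence on neither. The exploratory label lowers the weight of the point, but the change is cheap and this is the only quantitative evidence planned on pupils' satisfaction.

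**What to change.** In the Statistical analysis plan:

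- State how grade is handled, and replace the pooled chi-squared test with a grade-stratified comparison within school: a Cochran-Mantel-Haenszel type test, or an ordinal model with grade as a covariate.
- Report, by school, grade and round, the number of pupils invited and answering. For each item, report the change and its interval by grade.
- Add a grade-by-round comparison, because the stratified test alone does not show opposite reactions.
- State that in a school with only one of the two grades the comparison reduces to that grade.

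The cost is mainly SAP wording, provided that grade is recorded with each answer. The documents do not confirm this, and the sponsor should. The stratified test loses almost no power. Grade-specific intervals are about 40% wider with equal grades, and five comparisons per school become ten, so the grade-specific results should be read as estimates rather than as separate tests. Selective response within a grade remains uncorrected; response counts would help to show it, and linking each pupil's two answers would be needed to address it.

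### For the eight daily kitchen outcomes and five satisfaction items, the SAP describes no estimate across schools to answer a hypothesis posed once for the menu

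*Combined protocol and SAP*

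**What the plan says.** The Introduction states one hypothesis for the whole study: "Our hypothesis is that school meals can be optimized to be nutritious and more climate friendly, without negatively affecting acceptance, food waste and cost". The Design section sets the ITS comparison "on daily food waste and consumption at school level".

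The Statistical analysis plan repeats this: "ITS analysis will be implemented at school level to assess the difference between the two periods daily", for eight daily outcomes (pupil count, kitchen waste, prepared food, serving waste, and plate waste and consumption, each as a total and per pupil). On the regression it says "These models will be determined by three independent variables": time, period, and time by period. There is no school term, random effect or weighting. The five satisfaction questions are compared by Pearson's chi-squared "within each intervention school".

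The document gives no pooled model, no step that combines school results, and no rule for reading schools that differ. It also gives no primary outcome, alpha level, power statement or number of schools.

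**The concern.** The question is whether the optimized menu changes waste, consumption and satisfaction. As written, the answer arrives as a set of school-by-school results. With three schools, for example, there would be 8 × 3 = 24 level-change estimates and 5 × 3 = 15 chi-squared tests, and none of them addresses the menu overall.

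Two problems follow. If one school shows a significant change and another does not, the plan offers no agreed reading, and emphasis can be chosen after the fact. And because the hypothesis is that nothing gets worse, a finding of no significant change in any school could be taken as support when it may only reflect wide intervals. What the hypothesis needs is an overall estimate with an interval showing how large a deterioration can be excluded.

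**Working it through.** The documents give no power, SD or effect size, so there is no planned figure to reproduce. The check asks how much one school's regression can show and how much a combined estimate would add.

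**Inputs**
- From the Design section: four weeks of baseline, a two-week break, four weeks of intervention. Five school days a week (assumed) give 20, 10 and 20 days.
- From the SAP: an intercept plus three terms, so 40 − 4 = 36 residual degrees of freedom per school.
- Assumed: independent daily errors, residual SD = 1, two-sided alpha 0.05, 2 to 6 schools of equal precision.

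**1. Standard error of the level change in one school.** At the first intervention day this is the intervention line minus the baseline line extended to that day. Each line has variance 1/20 + d²/665, where 665 = 20 × (20² − 1)/12 and d is the distance in days from that period's midpoint.
- Intervention line, d = 9.5: 0.05 + 90.25/665 = 0.186.
- Baseline line with the break counted, d = 20.5: 0.05 + 420.25/665 = 0.682.
- Baseline line with measured days numbered consecutively, d = 10.5: 0.05 + 110.25/665 = 0.216.
- SE = √(0.186 + 0.682) = 0.93, or √(0.186 + 0.216) = 0.63.

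**2. What one school can show.** The 95% half-width is 2.028 × SE = 1.89 or 1.29 SD. The change detectable with 80% power is about 2.88 × SE = 2.7 or 1.8 SD.

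**3. Agreement between three schools sharing a true 1 SD change.** Power per school is p = 0.181 or 0.336. With errors independent between schools, the chance that the significance verdicts are not all the same is 1 − p³ − (1 − p)³:
- break counted: 1 − 0.006 − 0.548 = about 45%;
- not counted: 1 − 0.038 − 0.293 = 67%.

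The chance that none of the three is significant, although all truly changed, is 55% or 29%.

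**4. What pooling adds.** For k schools with a fraction r of the daily variance shared between them, SE(k) = SE × √[(1 + (k − 1)r)/k]. The detectable change is about 2.84 × SE(k) for k = 2 and 2.81 × SE(k) for k = 6.

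| Shared variance | Break | SE, k = 2 to 6 | Detectable change |
|---|---|---|---|
| none | counted | 0.66 to 0.38 | 1.9 to 1.1 SD |
| none | not counted | 0.45 to 0.26 | 1.3 to 0.7 SD |
| half | counted | 0.81 to 0.71 | 2.3 to 2.0 SD |
| half | not counted | 0.55 to 0.48 | 1.6 to 1.4 SD |

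**5. Where the imprecision comes from.** A plain difference of two 20-day means in one school has SE √(2/20) = 0.32. The pooled segmented model for three schools with independent errors still has 0.93/√3 = 0.54 with the break counted (0.63/√3 = 0.37 without). Fitting slopes to short series, and extending the baseline slope across the break, costs more than the failure to pool. The mean difference ignores trend, so it serves here as a diagnostic and not as a substitute analysis.

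**6. Careless pooling.** If three schools share day-to-day variation and the pooled model ignores it, the simulated type I error at a nominal 5% is 11%, 17% and 22% for 25%, 50% and 75% shared variance. The approximation 2{1 − Φ(1.96/√(1 + 2r))} gives 11.0%, 16.6% and 21.5%.

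**The case against.** Much of the case on the other side stands and limits the point.

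- A reader might infer that the SAP explicitly fits a separate ITS in each school. It does not say so. The wording could mean data aggregated to the school rather than to the pupil. Separate fits are the natural reading because the model has no school term, but only the satisfaction tests are expressly per school. On either reading, no combined estimate is described.
- A reader might infer that every study outcome is affected. The point covers the eight ITS outcomes and five satisfaction items. Climate impact and cost have no statistical analysis in the SAP, and the focus groups use content analysis. The hypothesis has several parts, and a pooled waste model answers only some of them.
- A reader might infer that the per-school satisfaction tests are underpowered. That cannot be shown: respondent numbers are not given, the questions are multiple choice, and no dichotomy is defined. The SAP also describes this analysis as exploratory.
- A reader might infer that pooling would make the study precise. Steps 4 and 5 show that it would not. If much daily variation is shared, the gain is modest.
- A reader might take a shared dish effect as given. The documents do not state that schools serve the same dishes on the same days.

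It can also be argued that with few schools, school-specific reporting is reasonable and a common change is an assumption. That is fair, and it is a reason to keep the school results beside the combined one. It is not a reason to leave the overall question without an estimate.

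**Conclusion.** The point holds in this limited form. For thirteen quantitative outcomes the SAP offers no overall estimate or interval to answer a hypothesis about the menu across schools. With ITS intervals of about ±1.9 or ±1.3 residual SD per school, discordant or uniformly non-significant school results are likely even when schools respond alike. A combined estimate is a real but partial improvement, and its size depends on the number of schools and on how much daily variation they share, neither of which is stated.

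The figures rest on five-day weeks, independent errors within a school, equal precision across schools and two-sided 5% tests. Positive autocorrelation would widen the per-school intervals: at 0.2 to 0.4 the half-width becomes 2.24 to 2.64 SD with the break counted, or 1.48 to 1.62 without. True differences in effect between schools would reduce the gain from pooling.

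**What to change.** In the Statistical analysis plan:

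1. State outright that the ITS is fitted per school, if that is the intention.
2. Add one combined estimate with a confidence interval for each ITS outcome. Use a joint segmented regression on a per-plate or log scale, so that schools of different size are comparable, with school-specific intercepts and baseline slopes and a common level and slope change.
3. If schools serve the same menu on the same days, allow for errors shared by day, through a menu-day random effect or standard errors clustered by day. If they do not, this term is unnecessary.
4. Keep the school-specific estimates beside the combined one to show heterogeneity.
5. For each satisfaction item, add one school-stratified estimate or test (for example Cochran-Mantel-Haenszel) beside the per-school chi-squared tests.

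The cost is SAP wording, one extra model per ITS outcome and one extra analysis per satisfaction item, with no new data. The downside is that the combined result describes the average of the study schools only and assumes a common change. The report should say both.
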